13. DATA ANALYSIS AND MONITORING	20
13.1. Sample Size Determination	20
13.2. Planned Statistical Analysis	21
13.2.a Primary Analysis.....	21
13.2.b Secondary and Exploratory Analyses	21
13.3. Data and Safety Monitoring	22
14. REFERENCES	24

PROTOCOL SUMMARY

Title: Serologic Response to a New Recombinant, Adjuvanted Herpes Zoster Vaccine in Patients with Chronic Lymphocytic Leukemia and Waldenström Macroglobulinemia Treated with First-Line BTK Inhibitors – A Pilot Study

Objectives:

The primary objective is to measure humoral response 4 weeks after vaccination with the Shingrix herpes zoster vaccine in patients with CLL and WM undergoing first-line treatment with BTK inhibitors.

The secondary objectives of the study are:

- To measure the humoral immune response at 24 months after the completion of vaccination with the Shingrix vaccine in patients ≥ 50 years with CLL and WM receiving first-line treatment with BTK inhibitors.
- To measure PBMC activation by ELISPOT and/or flow cytometry at 4 weeks and 24 months following vaccination with Shingrix, as a marker of cellular mediated immunity.
- To determine the rate of lymphoma progression while receiving BTK inhibitors.
- To correlate lymphoma progression while receiving BTK inhibitors and vaccine response at 4 weeks and 24 months following the vaccination.

Study Population:

Male and Female, ≥ 50 years of age, with diagnosis of chronic lymphoid leukemia (CLL) or Waldenstrom's macroglobulinemia (WM). See full inclusion/exclusion criteria in section 3. 2.

Number of Subjects:

33

[figure not shown]
Description of Study Intervention:

Administration of Shingrix vaccine at baseline and 2 months and performance of blood draws at baseline, at 4 weeks and 24 months after the completion of vaccination to assess serological response.

Study Duration:

Approximately 26 months

STUDY DIAGRAM

1. PURPOSE OF THE STUDY AND BACKGROUND

1.1. Purpose of the study

Chronic lymphocytic leukemia (CLL) and Waldenstrom's macroglobulinemia (WM) are known risk factors for zoster reactivation, commonly called shingles. Although a recently FDA-approved recombinant, adjuvanted herpes zoster vaccine (Shingrix) is currently being offered to these populations, no study has specifically evaluated them in combination with BTK inhibitors.

The purpose of the study is to complete a single-arm trial evaluating if patients with CLL or WM, while on treatment with first-line BTK inhibitors, can achieve immunologic response to Shingrix. If effective, this will result in a new, well-tolerated shingles prevention strategy for these patients.

Primary objective:

- To measure the humoral immune response 4 weeks after the completion of vaccination with the Shingrix vaccine in patients \geq 50 years with CLL and WM receiving first-line treatment with BTK inhibitors.

Secondary objectives include:

- To measure the humoral immune response at 24 months after the completion of vaccination with the Shingrix vaccine in patients \geq 50 years with CLL and WM receiving first-line treatment with BTK inhibitors.
- To measure PBMC activation by ELISPOT and/or flow cytometry at 4 weeks and 24 months following vaccination with Shingrix, as a marker of cellular mediated immunity.
- To determine the rate of lymphoma progression while receiving BTK inhibitors.
- To correlate lymphoma progression while receiving BTK inhibitors and vaccine response at 4 weeks and 24 months following the vaccination.

1.2. Background

Varicella zoster is a ubiquitous virus in the United States that initially manifests as chicken pox in children. Once a person has been infected, the virus remains latent and can reactivate on various occasions, especially when immunity decreases. This herpes zoster reactivation, commonly called "shingles", is a painful condition which can lead to permanent nerve damage, pain, costly treatment and, on very rare occasions, death.

Herpes zoster reactivation is common in the general population, with rates averaging 3.2 cases/ 1000 person years. The incidence increases as people age, reaching 10.9 cases/ person years over the age of 80.¹ Since 2006, a live-attenuated vaccine has been indicated for people over 50 years of age to prevent zoster reactivation. Because of pre-existing immunosuppression, this vaccine is contraindicated in patients with hematologic malignancies, namely CLL and WM.

Yet, we know that these patients suffer from increased risk of developing zoster reactivation. A recent British study found that patients with hematologic malignancies had a 2.46-fold increased risk of developing shingles and among them, lymphoma was the most represented

subgroup.² An American database study showed similar results.¹

In October 2017, the FDA approved the use of a new recombinant, adjuvanted vaccine to prevent shingles in patients over 50 years old. This vaccine has shown greater efficacy at creating immune response than the former live-attenuated vaccine in healthy patients, and has now become a better prevention option in patients over 50 years old.³ In that population, the capacity to mount immune response was observed in almost 100% of patients one month after the last of the two doses.³

Patients with hematologic malignancies represent a distinct class of patients because of their baseline immune alterations, in part due to dysfunctions in the B-cell receptor (BCR) pathway.⁴ Among indolent lymphomas, CLL has most frequently been associated with acquired immunodeficiency and infections are a major cause of morbidity and mortality in these patients.⁵ Mechanisms for that state of immunodeficiency are diverse and not completely understood, but include, in addition to alterations in the BCR pathway, marked dysfunction of the immune system via alterations in T-cell repertoire and hypogammaglobulinemia.^{6,7} As a result, immunogenicity to various vaccines is also reduced.^{8,9,10,11}

Despite these characteristics, patients with hematologic malignancies receiving treatment with anti-CD20 monoclonal antibodies have been shown to achieve immune response to inactivated zoster vaccination¹² and a recent large phase 3 trial showed reduction in herpes zoster reactivation and persistent neurologic pain with the same vaccine.¹³ However, among that population, patients with indolent lymphoma were those with the lowest response rate.¹² Patients with hematologic malignancies undergoing autologous stem cell transplants have also been shown to achieve serologic response to Shingrix in a recent study.¹⁴

Over the last few years, novel therapies have emerged for the treatment of CLL¹⁵ and WM^{16–18}, including Bruton tyrosine kinase inhibitors of which ibrutinib and acalabrutinib are examples. Bruton tyrosine kinase (BTK) is thought to play an important role in the biology of these diseases.¹⁹ Its constitutional activation leads to activation of several downstream pathways, including MAP kinase, AKT and NFkB, resulting in cell proliferation, differentiation and survival.⁴

BTK also plays a significant role in normal immune defense. Congenital lack of BTK activity results in X-linked agammaglobulinemia, a condition characterized by altered humoral immunity and impairment in T cell memory response. Affected patients present with severe infections caused by increased susceptibility to encapsulated bacteria and certain blood borne viruses.¹⁹

Some data indicate that CLL patients treated with BTK inhibitors manage to reconstitute partial immune response with increased levels of immunoglobulins, suggesting that the treatment helps control the immune alterations due to the disease rather than amplify them²⁰. Despite this, immunogenicity to certain vaccines is difficult to achieve.^{21,22}

To our knowledge, there are no prospective studies that have evaluated if patients while on treatment with single agent BTK inhibitors could achieve immune response to a zoster recombinant vaccine. We hypothesize that patients with CLL and WM while on treatment with BTK inhibitors can achieve a humoral response, albeit to a lesser level than the general population.

2. STUDY DESIGN

2.1. Overview

We are conducting a single-center, single-arm pilot clinical study. All subjects will be provided with the study vaccine.

Anticipated enrollment period: We anticipate meeting enrollment goals within 6 months.

Follow-up period: Patients will be treated and followed on study for 24 months post-completion of vaccination for assessment of lymphoma status and possible evaluation of persistent serologic response.

2.2. Rationale for Study Design

Evidence exists that patients over 50 years old in the general population and immunocompromised patients with hematologic conditions can achieve serologic response to Shingrix.³ However, response seems to be less in patients with CLL or indolent lymphoma¹³ and patients treated with BTK inhibitors have yet to be studied. Our study specifically targets that population through a simple trial that will address whether these patients can truly benefit from the vaccine.

The vaccine is indicated in our planned patient population, but we do not understand its efficacy and we do not know optimal timing for vaccination while on BTK inhibition. There is evidence of vaccine response in a subset of immunocompromised patients with minimal toxicity.^{13,14} A placebo group was not included because it was perceived as possibly unethical to take away their possibility to receive the vaccine.

The decision was also made not to include a healthy control group since the primary objective of the study is to assess the response rate in our population, not to compare it with the general population. Moreover, a study with over 3000 healthy patients shows robust response data in almost 100% of subjects, which we can use to indirectly compare our response rates.³ Prior studies in vulnerable populations have used the same design with valid results. Toxicity rates did not result any higher than in the general population in these studies. It is not expected to be higher in our population.

Assessment of serological response at four weeks was planned in our study in accordance with previous vaccination literature. This time point is known to represent the end of primary immunity response, which is a marker of immunologic response. Assessing a clinical endpoint (reactivation of herpes zoster) would have necessitated a larger cohort of patients followed for several years, which is not the objective of a pilot study. This could ultimately be done in further studies if response is noted in this trial.

Reassessment of serological response was originally planned at one year to evaluate the rate of persistent response. This time point was previously chosen in the general population, and subjects were found to have persistent immunity.³ It was also assessed in a recent phase III trial evaluating response to another inactivated herpes zoster vaccine in immunocompromised patients undergoing autologous stem cell transplant. They were also found to have persistent response.¹³ Due to the COVID-19 pandemic and closure of research laboratories the one year sample could not be collected. The sample will instead be collected at 24 months \pm 3 months. A recent study demonstrated persistent response to the Shingrix vaccine in healthy adults up to 10

years after the initial dose³⁴, suggesting that the 24-month collection is a reasonable time point for reassessment.

This study is designed to obtain valid and comparable results to measure response to a vaccine in a vulnerable population in a fast and uncomplicated way.

2.3. Rationale for Dosage

The FDA approved the use of the new recombinant, adjuvanted herpes zoster vaccine (Shingrix) in October 2017. The vaccine is supplied as a single-dose vial of lyophilized varicella zoster virus glycoprotein E (gE) to be reconstituted with the accompanying vial of AS01B adjuvant suspension component. After reconstitution, a single dose of Shingrix is 0.5 mL and should be administered intramuscularly.

Two doses at 0 and 2 to 6 months are indicated.

3. CHARACTERISTICS OF THE RESEARCH POPULATION

3.1. Subject Characteristics

a) Number of Subjects:

Target accrual is 30 evaluable CLL or WM subjects receiving treatment with BTK inhibitors. Assuming a 10% drop out rate, we aim to enroll a total of 33 subjects. Participants will be replaced in case of drop out or failure to receive the second dose of the vaccine. Failure to have blood drawn for baseline and/or 4 weeks after vaccination will also warrant replacement.

Subjects will not be replaced if they fail to present to the blood draw 24 months post-vaccination.

In the case of a change of therapy between the first and second dose of the vaccine (including the addition of rituximab), patients will remain on study and will not be replaced. Their data will be included in the estimates of vaccine response in the intent-to-treat analysis but excluded from sub-group analyses.

Based on data from the University of Rochester Cancer Center pharmacy, as of May 2018, 150 CLL and WM patients are on BTK inhibitor therapy and there are approximately 20 new cases per month. A local CLL database confirms those numbers and shows that a total of about 50 patients are on single-agent, first-line ibrutinib as of January 2018. No patient was identified while collecting this data, with respect to patients' confidentiality.

Patients who have started BTK inhibitors come to clinic about every 3 months for routine visits. Based on those numbers, we expect the recruitment of 33 patients to be feasible within 6 months.

b) Gender and Age of Subjects:

Subjects must be at least 50 years old to participate. Patients under 50 years old are excluded as per the label of the vaccine. It is anticipated that most subjects will be in their sixth or seventh decade given the age distribution of CLL²³ and WM.²⁴ There is no upper age limit if the patient meets the other inclusion criteria.

We expect that only a minority of subjects will be diagnosed with WM as compared to CLL because it is a much rarer disease, with only 1400 new cases diagnosed each year in the United States.^{25,26}

All genders are accepted. It is expected that there will be slightly more males than females included in the study as the male-to-female ratio in CLL is normally 1.3-1.7.²⁷ and about 60% of WM patients are males.²⁴

c) Racial and Ethnic Origin:

We are not excluding any persons on the basis of racial background. The incidence of CLL in the United States is highest in Caucasians as compared with African Americans and Asian Pacific Islanders.²⁸ WM is also more common in Caucasians than in any other ethnic groups, particularly in Hispanics and in African Americans where it makes up only about 5% of the population.²⁵ This should be reflected in our study.

d) Vulnerable Subjects:

Vulnerable subjects should not be enrolled.

3.2. Inclusion and Exclusion Criteria

a) Inclusion Criteria:

Patients will be eligible if:

- They are at least 50 years of age;
- Have been diagnosed with chronic lymphocytic leukemia (CLL) OR Waldenström macroglobulinemia (WM);
- Have been on first-line BTK inhibitor (i.e. ibrutinib or acalabrutinib) for at least 3 months;
- Prior treatment with single agent rituximab is permitted if the last dose was administered more than one year ago;
- Have at least a one-year life expectancy;
- Have a history of varicella (chicken-pox) OR lived in the US or any endemic country for > 30 years'
- Prior radiation therapy is allowed

b) Exclusion Criteria:

Patients will be excluded from the study if they:

- Have a known hypersensitivity to a vaccine component;
- Have had herpes zoster reactivation within the past year;
- Received or were scheduled to receive a live virus vaccine in the period from 4 weeks prior to Dose 1 through 28 days post-second dose;
- Received or were scheduled to receive an inactivated vaccine in the period ranging from 7 days prior to Dose 1 through 7 days post-second dose;
- Are unable to give informed consent;
- Have an absolute lymphocyte count greater than $20,000 \times 10^9/L$;
- Are receiving treatment for CLL or WM with an additional agent other than a BTK inhibitor;

- Had rituximab treatment less than one year prior to study start;
- Had prior chemotherapy.

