3.3. Discussion of Subject Population

Inclusion and exclusion were selected to include a homogeneous CLL and WM population treated with BTK inhibitors. Special consideration was taken to avoid disease heterogeneity in order to obtain valid results and this is why only patients who have been on a first-line BTK inhibitor for at least 3 months will be included.

The age limit was set at 50 years old as per the vaccine label.

Exclusion criteria were the result of contra-indications to the vaccine or to the inability to correctly undergo all steps in the research process. In our population, a considerable number of patients also received concomitant rituximab for a period of 6 months (weekly for 1 month and monthly until month 6) at treatment initiation in the context of a clinical trial. We decided not to exclude these patients, but to restrict their enrollment to those who have not had rituximab in the last 12 months. The 12-month time limit was set to minimize the prolonged side effects of rituximab on immunity, but to maximize the inclusion of patients. Data published by Anolik et al in 2006 showed that, although incomplete, B cell recovery occurred by 12 months.²⁹ Even though retrospective data shows that 38.9% of patients with non-Hodgkin's lymphoma develop new-onset hypogammaglobulinemia at a median of 1.4 years post-treatment with a median of 7 doses of rituximab³⁰ and multiple case reports of prolonged hypogammaglobulinemia, happened in the context of rheumatologic diseases or concomitant chemotherapy,³¹⁻³³ this data does not represent our population and thus cannot be applied to them. Currently, no such data exists for this population.

Exclusion of subjects with absolute lymphocyte counts greater than 20,000 cells/ μ L was decided empirically to avoid interference with the assays. An excessive number of lymphocytes could potentially interfere with the laboratory analyses.

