5. METHODS AND STUDY PROCEDURES

Screening procedures will take place after subjects have consented to study participation.

Subjects will be asked to return to the clinic at a later date to have the baseline blood tests performed and the vaccine administered. We will determine a selection of dates where a certain number of patients will be able to have both procedures performed on the same day.

Blood may also be drawn for baseline testing at the Cancer Center and subjects subsequently administered the vaccine at the outpatient pharmacy on screening day.

After consent, a brief chart and CLL database review will be performed to collect certain variables such as those listed below:

- Age
- Stage at diagnosis
- Date of diagnosis
- 17p deletion (yes/no)
- TP53 mutation (yes/no)
- Mutated status of IVHG (yes/no)
- 11q del (yes/no)
- Presence of trisomy 12 (yes/no)
- Del 13q (yes/no)
- Watch and wait period duration
- Date of BTK inhibitor therapy initiation
- History of zoster reactivation

- History of zoster vaccination
- Immunoglobulin levels before study start
- Use of rituximab in the past (yes/no)
 - Number of cycles
 - Date of last cycle

Prior to the first dose of the vaccine, blood will be collected to assess immunity via measurement of anti-gE and cellular-mediated immunity. Samples will be processed in the cancer center research laboratory. Peripheral blood mononuclear cells (PBMC) will be processed and cryopreserved for future cellular assays and serum will be banked for analysis of anti-gE.

At visit 2, four weeks post-first dose, subjects will be contacted by phone call to report any adverse events. A chart review for severe adverse events will also be performed.

As per the label of the vaccine, the second dose of the vaccine will be administered two months after the first one, at visit 3. One month subsequent to that second dose, at visit 4, a second blood draw will be performed to evaluate the subject's immunogenic response. The initial analyses will be repeated, and response will be measured using statistical methods described below. Safety will be assessed again in the same way as after the first dose. A chart review will be performed to assess CLL/WM progression on BTK inhibitor therapy as determined by subjects' regular team of providers during their latest visit.

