These analyses will be repeated 24 months after the last dose of the vaccine to assess long term immunogenicity, at visit 5. A last chart review also be performed to assess incidence of zoster reactivation and disease progression as determined by their team of providers during the latest visit.

Table 1. Schedule of Study Procedures

Visit	Screen*	1*	2	3	4	5
		Dose 1	Safety assessment	Dose 2	Blood draw	Optional Blood draw
Visit window		0	Week 4 ± 1 week	Weeks 8-12	4 Weeks ± 1 week after Dose 2	24 months ± 3 months of Dose 2
Obtain informed consent	X					
Confirm eligibility	X					
Enroll	X					
Vaccine administration	X*	X*		X		
Lab work (anti-gE and CMI)	X*	X*			X	X
Safety assessment (patient-reported AEs)			X		X	

and chart review)						
-------------------	--	--	--	--	--	--

*Note: Administration of the first dose of the vaccine and completion of the lab assays will take place once, either at the screening visit OR at the first visit. If this is done at screening, then screening and visit one will happen within the same visit.

Subjects will be contacted through phone call OR in person at the clinic on for safety assessment.

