5.2. Efficacy Assessments

Vaccine response, as determined by blood antibody levels to the varicella virus glycoprotein E subunit (anti-gE), will be measured by ELISA. This humoral response will be assessed four weeks after vaccination is complete. In patients who were seropositive before the study, a positive response will be defined as at least a four-fold increase in geometric mean concentration (GMC) of anti-VZV gE antibody as measured per ELISA. Humoral response in seronegative patients at baseline will be defined as at least a four-fold increase from the lower detection limit of the anti-gE antibody assay.

Secondary efficacy objectives include:

1. Measure humoral response at 24 months post-vaccination, which is defined as persistence of anti-gE antibody above test threshold at 24 months.
2. Measure cell-mediated response to vaccination at one month and 24 months after vaccination.
3. Evaluation of CLL/WM progression on BTK inhibitor as determined by treating oncologist at latest assessment, and correlation between progression on BTK inhibitor and vaccine response at 4 weeks and at 24 months post-second dose.

Cellular-mediated response will be determined by measuring PBMC activation (by ELISPOT or flow cytometry) following stimulation with varicella glycoprotein E peptide. PBMC activation at 4 weeks and 24 months post dose will be compared to pre-vaccination activation levels.

a. Safety Assessments

Subjects will be educated to recognize immediate adverse reactions to the vaccine. Patient-reported signs of allergic or hypersensitivity reactions will be assessed and managed by the study team as needed. Only severe adverse effects will be captured in this study. Subjects will be contacted 4 weeks \pm 1 week after each dose of the vaccine for assessment and their chart will be reviewed at the same moment. Severe adverse effects are defined as any grades 3-5 adverse effects included in the CTCAE v5.0 classification.

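### The lymphocyte-count exclusion differs 1000-fold between Section 3.2 (20,000 × 10^9/L) and Section 3.3 (20,000 cells/µL), and the Section 3.2 figure read literally excludes no one

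*Combined protocol and SAP*

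**What the plan says.** Section 3.2, the list staff would use to decide eligibility, excludes patients who "Have an absolute lymphocyte count greater than $20,000 \times 10^9/L".

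Section 3.3 explains the choice of criteria and describes this one as "Exclusion of subjects with absolute lymphocyte counts greater than 20,000 cells" per µL. It says the limit was chosen empirically to protect the assays, and gives the reason: "An excessive number of lymphocytes could potentially interfere with the laboratory analyses".

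The assays in question are described in Sections 5 and 5.2. On sample handling, Section 5 says: "Peripheral blood mononuclear cells (PBMC) will be processed and cryopreserved for future cellular assays and serum will be banked for analysis of anti-gE". On the cellular endpoint, Section 5.2 says: "Cellular-mediated response will be determined by measuring PBMC activation (by ELISPOT or flow cytometry) following stimulation with varicella glycoprotein E peptide".

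No other section states a lymphocyte limit. Table 1 has a row for confirming eligibility at screening, but its laboratory row covers only anti-gE and cell-mediated immunity. The chart-review list in Section 5 does not name a lymphocyte count. That list is not exhaustive, being introduced with the words "After consent, a brief chart and CLL database review will be performed to collect certain variables such as those listed below".

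**The concern.** The same number, 20,000, is attached to two different units, and the units are not equivalent. The two sections therefore classify some patients in opposite ways, and nothing elsewhere in the document settles which applies.

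The criterion has a stated measurement purpose. It is there to keep high lymphocyte counts from disturbing the laboratory work, and that work produces the primary humoral endpoint (anti-gE by ELISA) and the secondary cellular endpoint (PBMC activation). These feed the response rates, geometric means and fold-changes in Section 13.2.a and the mixed model in Section 13.2.b. If the Section 3.2 limit was applied as written, patients whom Section 3.3 meant to keep out could be in all of those estimates. A reader or auditor working from Section 3.2 alone also could not tell whether enrolling such a patient was a protocol deviation.

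The reach is limited. Section 3.3 does not say which assay would be affected or by how much. Safety, disease progression and zoster reactivation do not depend on these assays, and the sample-size reasoning does not use this criterion.

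**Working it through.** **Inputs**

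- Section 3.2 limit: 20,000 × 10^9 per litre.
- Section 3.3 limit: 20,000 cells per µL.
- Conversion: 1 L = 10^6 µL.
- Evaluable subjects: 30 (Sections 3.1 and 13.1).

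**Step 1. Put both limits in both units**

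| Source | Per litre | As × 10^9/L | Per µL |
|---|---|---|---|
| Section 3.2 | 20,000 × 10^9 = 2 × 10^13 | 20,000 | 2 × 10^13 / 10^6 = 20,000,000 |
| Section 3.3 | 20,000 × 10^6 = 2 × 10^10 | 20 | 20,000 |

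Ratio: 2 × 10^13 / 2 × 10^10 = 1000.

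The Section 3.2 figure cannot be reproduced from Section 3.3. Any count above 20 × 10^9/L and up to 20,000 × 10^9/L is eligible under Section 3.2 and excluded under Section 3.3.

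**Step 2. Can any patient exceed the Section 3.2 limit?**

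The documents give no lymphocyte volume, so I assume 50 to 300 fL per cell (1 fL = 10^-15 L). Volume of cells per litre of blood = count per litre × volume per cell.

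- Section 3.2, low end: 2 × 10^13 × 50 × 10^-15 = 1.0 L.
- Section 3.2, high end: 2 × 10^13 × 300 × 10^-15 = 6.0 L.
- Section 3.3: 2 × 10^10 × 50 × 10^-15 = 0.001 L, up to 2 × 10^10 × 300 × 10^-15 = 0.006 L.

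At the Section 3.2 limit, lymphocytes alone would fill the entire blood volume or several times that. Across the assumed range the criterion as written excludes no one.

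**Step 3. Scale of one patient**

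Let r be the number of responders among 30.

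- Reclassifying one patient changes the rate by 1/30 = 3.3 percentage points.
- Removing one non-responder changes it by r/29 − r/30 = r/870. The largest value is at r = 29: 29/870 = 3.3 points.
- Removing one responder changes it by r/30 − (r − 1)/29 = (30 − r)/870. The largest value is at r = 1: 29/870 = 3.3 points.

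So 3.3 points is the most that one such patient can move the observed response rate. It is a scale for any single patient, not an estimate of bias from this criterion, and it does not carry over to titers, fold-changes or cellular markers.

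**The case against.** The strongest reply is that this is a plain unit slip with no practical effect. The number is identical in both places, the very next section restates it in a workable unit with its purpose, and a limit that nobody can exceed is unlikely to have been used by a single-center team with lymphoma specialists involved. That is probably what happened, and it is why no wrong enrolment is alleged. It does not make the text correct: the error sits in the operative eligibility list, and the intended limit has to be inferred from the rationale.

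A second reply is that harm is not shown. Section 3.3 speaks only of possible interference, the primary endpoint is measured on serum, and no section explains how a high lymphocyte count would disturb a serum ELISA. This stands. The size of any effect is unknown and may be nil, and the 3.3-point figure does not change that.

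A third reply is that silence in the chart-review list and in the laboratory row of Table 1 proves little, since eligibility is confirmed in a separate row and the chart list is open-ended. This also stands. The silence shows only that the document cannot tell us which limit was used, so the answer must come from the screening records.

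Finally, the statement that Section 3.2 excludes no one depends on an assumed cell volume, not on a figure in the documents. It holds throughout the assumed range, and the 1000-fold contradiction stands without it. The exponent in Section 3.2 should be confirmed against the source PDF.

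**Conclusion.** The concern holds. Sections 3.2 and 3.3 state the same exclusion with limits that differ by a factor of exactly 1000, and no other text reconciles them. That conclusion rests only on unit conversion.

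The further statement that the Section 3.2 limit is empty in practice rests on the assumed 50 to 300 fL cell volume. The effect on results cannot be sized, because the documents do not say how many patients, if any, lie above the Section 3.3 figure. The point should be fixed because it is a certain error in a working eligibility rule that the protocol itself ties to the quality of its assays. It is not evidence that the results are biased.

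**What to change.** 1. Reconcile Sections 3.2 and 3.3 and state the limit in the same unit in both. Section 3.3's own figure is equal to 20 × 10^9/L; the sponsor should confirm which limit was intended.
2. Confirm from the screening records which limit was applied to the roughly 33 enrolled subjects.
3. Only if any enrolled subject exceeded the Section 3.3 figure, list those subjects and report the humoral and cellular response estimates with and without them.

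The cost is a one-line text correction and a check of about 33 screening counts. The sensitivity listing is short and may not be needed. Sample size and the planned analyses stay as they are.
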